Stage 2 - umbilical cord blood sampling. It is performed by a transfusion doctor of the State Budgetary Institution "MC Dynasty".

The selection criteria for the sample will be the following parameters:

1. Blood group compatibility by system AB0 and Rh
2. Infectious safety (negative HIV test results, hepatitis B and C, syphilis, herpes simplex virus, cytomegalovirus, toxoplasmosis)
3. No bacterial or fungal contamination.
4. Number of hematopoietic cells (mononuclears) in the range of 20-50 million cells per kg of patient weight.

Stage 3 - intravenous injection of hematopoietic cells in umbilical cord blood.

Preliminary examination of the patient and relatives:

- a) Determination of immune status by flow cytometry (SD3; SD4; SD8; SD19; SD16-56) - patient.
- b) Determination of cytokine levels in peripheral blood: interleukin 1 beta, interleukin 6, tumor necrosis factor alpha, interleukin 8, gamma-interferon - patient.
- c) Determination of HLA genotype by loci A, B, DRB1 - patient and parent, sibling.

The sample consists of a suspension of hematopoietic cells diluted in 10 ml 0.9% NaCl + 10 ml 6% hydroxyethyl starch in a disposable syringe labeled by the manufacturer (label).

The patient is injected in drops with the use of infusion. The rate of administration is 60 - 70 ml per hour. Immediately at the beginning of injection, a biological compatibility test should be performed.

Three-fold injection is planned at an interval of 1 month.

Possible area of application

Specialized hospitals.

Data to be obtained during implementation

- correct selection of criteria for selecting patients for treatment of patients with autism type disorder;
- developed algorithm for using the method of transfusion of hematopoietic cells of umbilical cord blood in complex therapy of patients with autism type disorders;
- information on the efficacy and safety of treatment of patients with autism-type disorder by transfusion of hematopoietic cells of umbilical cord blood;
- appropriateness and effectiveness of this method of treatment. To evaluate its impact on treatment tactics and results;
- Association of HLA genes with the development of autism spectrum disorders;
- relationship between immune status and cytokine profile and severity of the disease.

Therapy evaluation criteria

Evaluation of the effect of treatment is carried out 1, 2, 3 and 6 months after treatment.

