Evaluation of the effect is carried out using the scales used in the introduction to the protocol, evaluation of the neurological and psychological status of the patient.

Evaluation of immune status indicators is carried out 6 months after the last injection.

Cytokine profile is assessed 1, 2, 3 months after the first injection.

Expected results:

It is assumed that transfusions of hematopoietic cord blood cells in patients with autism spectrum disorders will not cause adverse reactions and complications (safe) and will lead to improved social interaction and communication of patients, increased social adaptation, reduced stereotyping, increased self-service skills, increased cognitive functions.

STATISTICAL CONSIDERATIONS

This study will enroll autistic children age 3 to 15 years of age.

Participants will be carried out on 10 patients with autism spectrum disorder by transfusion of hematopoietic cord blood cells. As a control group, 10 patients with a similar pathology will be examined, comparable in age, gender and degree of autistic disorder according to the “paracopy” type against the background of standard therapy.

This is interventional, prospective, non-randomized with a control group study with three intravenous allogeneic, unrelated CB infusion in children ages 3-15 years with ASD/

The primary outcomes will be assessed 1, 2,3,6 and 12 months after the initial infusion in the sequence. Duration of study participation will be 12 months from the time of baseline infusion.

Accrual

It is estimated that up to 2-3 research participants will be enrolled each week and that approximately 4 weeks of accrual will be necessary to enroll 10 participants.

Study Duration

Research participants will be followed for safety for 12 months after the third study infusion.

Demographics and Baseline Characteristics

Demographics and baseline characteristics will be summarized for all research participants. Characteristics to be examined include age, sex, and baseline behavioral status (ATEK).

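### The stated participation period ends about 2 months before the stated safety follow-up, and the visible text specifies no adverse-event recording or count

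*Combined protocol and SAP*

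**What the plan says.** **Duration.** Stage 3 of the Treatment protocol states "Three-fold injection is planned at an interval of 1 month". Statistical Considerations gives the outcome schedule, "The primary outcomes will be assessed 1, 2,3,6 and 12 months after the initial infusion in the sequence", and directly after it the participation period, "Duration of study participation will be 12 months from the time of baseline infusion". Study Duration then states "Research participants will be followed for safety for 12 months after the third study infusion".

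The other dated assessments are under Therapy evaluation criteria:
- For the treatment effect, the plan says "Evaluation of the effect of treatment is carried out 1, 2, 3 and 6 months after treatment".
- For the immune panel, it says "Evaluation of immune status indicators is carried out 6 months after the last injection".
- For the blood cytokines, it says "Cytokine profile is assessed 1, 2, 3 months after the first injection".

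**Safety.** Safety stands beside efficacy in Clinical Purposes, in item 3 of the Tasks, and among the data the study is meant to yield. Item 3 names rating scales as the means of analysing both. Research methods names two scales, CARS and ATEC, for following change, and adds neuropsychological, speech and neurological examination, immune status, cytokines and HLA typing. At the infusion itself, Stage 3 requires one check: "Immediately at the beginning of injection, a biological compatibility test should be performed". Expected results anticipates no adverse reactions or complications. The statistical text refers generally to parametric and non-parametric methods, names the Wilcoxon and Mann-Whitney tests, and presents data as medians with quartiles.

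**The concern.** There are two linked problems.

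First, the two periods run from different starting points, both explicit, and do not fit together. A site that closes a child's participation at month 12 has not completed the safety follow-up that the plan promises. A site that continues to month 14 has gone past the stated participation period, with no contact scheduled for it.

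Second, safety is part of the purpose, but the one means named for analysing it is a pair of behavioural scales. These do not detect a transfusion reaction or an infection. If events are not recorded by rule, an unrecorded event looks the same as no event. The plan's expectation of no adverse reactions could then appear confirmed by default after 30 infusions (10 children x 3) of unrelated donor cord blood.

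**Working it through.** **Inputs.** Three infusions, 1 month apart (Stage 3). Participation of 12 months from the first infusion and 10 treated children (Statistical Considerations). Safety follow-up of 12 months from the third infusion (Study Duration).

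**Step 1: end of safety follow-up.**
- Third infusion: (3 - 1) x 1 month = month 2.
- End of safety follow-up: 2 + 12 = month 14.
- End of participation: 0 + 12 = month 12.
- Shortfall: 14 - 12 = 2 months, which is 2/12 = 17% of the stated follow-up.
- Follow-up after the third infusion that fits within participation: 12 - 2 = 10 months.

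The stated 12-month participation is therefore not reproduced from the other two statements. The periods agree only if all three infusions fall at month 0, which the 1-month interval rules out.

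**Step 2: is any dated visit later than month 12?**

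| Assessment | Months from first infusion | Last |
|---|---|---|
| Primary outcomes | 1, 2, 3, 6, 12 | 12 |
| Effect evaluation, counted from first infusion | 1, 2, 3, 6 | 6 |
| Effect evaluation, counted from third infusion | 3, 4, 5, 8 | 8 |
| Immune status | 2 + 6 = 8 | 8 |
| Cytokines | 1, 2, 3 | 3 |

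The latest dated visit is month 12 under either reading of the effect evaluation. The month-14 end point has no visit attached to it.

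**Step 3: which planned items could serve as adverse-event data?**
- CARS and ATEC: behavioural, so they cannot register reactions or infections.
- Compatibility test: a check at the start of the injection, with no stated rule for recording events during or after it.
- Infection screening in Stage 2: applies to the cord blood sample, not to the child afterwards.
- Blood, urine and stool tests in Stage 1: done at selection, with no repeat stated.
- Neurological, immune and cytokine follow-up: may bear on safety, but with no rule for identifying or counting an event.
- Wilcoxon and Mann-Whitney tests: used for change scores and group comparisons; the statistical text assigns no summary to adverse events.

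**Step 4: contacts already planned for a treated child** (infusions and visits at months 1 and 2 assumed to coincide).
- Effect evaluation counted from the first infusion: months 0, 1, 2, 3, 6, 8, 12 = 7 contacts; 7 x 10 = 70 forms.
- Counted from the third: months 0, 1, 2, 3, 4, 5, 6, 8, 12 = 9 contacts; 9 x 10 = 90 forms.
- Controls, assuming they attend the outcome visits at months 1, 2, 3, 6 and 12: 5 x 10 = 50 forms.

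**Step 5: what zero events would show.** With 0 of 10 children affected, the exact two-sided 95% upper limit is 1 - 0.025^(1/10) = 0.308, about 31%.

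**The case against.** The strongest reply on duration is that the participation sentence follows the outcome schedule directly and may describe only that schedule, with safety follow-up meant to run on. On that reading no follow-up need be lost, and no named analysis uses months 12 to 14. This is fair, and it limits the consequence. It does not remove the error: the participation sentence would still be wrong as written, and the late contact would still be unscheduled. A reader might infer that two months of safety data will be lost. The documents do not settle that; they show only that the two statements cannot both hold.

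On safety, the reply is that the plan is not empty. Neurological status, immune status and cytokines are assessed, and after an unrelated-donor infusion these could inform safety. That stands. A reader might infer that the plan contains no safety assessment at all, and the documents do not support so broad a claim. The supported claim is narrower: no recording or count of adverse events is specified. Some pages were also removed before review, so even this absence is shown only for the visible text.

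A third reply concerns group comparison. Treated children have 7 to 9 planned contacts, and controls have 5 on the assumption above. Events during an infusion have no counterpart in controls. Comparing event proportions over all contacts would favour finding more events in the treated group. This objection is right, and it shapes the fix.

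Finally, an interval on 10 children is wide. That is true, but it is also a reason to show it: a bare zero would suggest more reassurance than the data can give.

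**Conclusion.** Both parts hold, with different degrees of certainty.

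The duration conflict is certain from the text: about 2 months, or 10 months of available follow-up against 12 stated. It rests only on the 1-month infusion interval being kept. Taken alone it is a wording correction with a small consequence.

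The safety gap matters more for interpretation, but it rests on the visible text only. The named rating scales cannot carry the safety analysis, and nothing visible specifies how adverse events are to be recorded or counted. The planned neurological, immune and cytokine measures do not fill that gap. The efficacy design and tests are not affected.

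**What to change.** **Duration.** Choose one:
- State participation as about 14 months for treated children, with one safety contact, for example by telephone, at about month 14. Cost: 10 extra contacts.
- Restate safety follow-up as about 10 months after the third infusion. Cost: a slightly less favourable stated follow-up.

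**Safety.**
- In item 3 of the Tasks, confine the rating scales to efficacy.
- Record adverse events on one form at each infusion and each visit already planned. This is about 70 to 90 forms for treated children, depending on which infusion the effect evaluation is counted from, plus 10 if the month-14 contact is added.
- Report the number of treated children with at least one event out of 10, with an exact 95% confidence interval.
- Keep any control-group figures descriptive and restricted to visits common to both groups. If controls attend all five outcome visits, this adds 50 forms.

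The cost is a few changed sentences and modest form work. It would also help to say which infusion the effect evaluation is counted from, since that fixes the number of forms.

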To assess the therapeutic efficacy of using core blood cells, during the research studies the CARS, CGI and ABC scales were used. CARS provides descriptive information about pathological behaviour and classifies severity in children with autism, while the CGI scale, as a global measure, indicates a noticeable overall treatment effect. However, further research will need to extend the rating scales to standardize the diagnosis and treatment of autism in detail.

In 2011, a Chinese research group from the Shenzhen Beike Bio-Technology Co. conducted a scientific clinical research study of the use of intravenous mononuclear cord blood cells in patients diagnosed with autism. In total, 37 patients aged 3 to 12 years were tested. There were 3 clinical groups: Group 1 consisted of 14 patients receiving the injections of mononuclear cord blood cells

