at a dosage of 2 million cells per 1 kg of patient weight (1 intravenous injection, 3 intrathecal with an interval of 5-7 weeks). Group 2 consisting of 9 patients receiving the injections of mononuclear cord blood cells at a dosage of 2 million cells per 1 kg of patient weight and mesenchymal stem cells at a dosage of 1 million cells per 1 kg of patient weight (2 intrathecal and intramuscular injections and 2 intrathecal injections solely). Patients of Groups 1 and 2 received standard rehabilitation therapy. Group 3 consisted of 14 patients receiving standard rehabilitation therapy. The evaluation was conducted 24 weeks after the course of injections. During the treatment, all patients had normal and stable vitals. At the periods of injections or period after them. No allergic or immunological reactions were observed in any patient. There were no deviations from the normal ranges or significant changes in the laboratory indicators of the liver and kidneys functioning, in comparison with the initial level (ALAT, ASAT, bilirubin, urea, and creatinine). Evaluation of the psychological status was made on the CARS scale. The total CARS score was significantly reduced in the Group 2 (a decline of 37.9%); in Group 1, the indicator decreased by 20.0%; in Group 3, i.e. the control group, the indicator decreased by 13.7%. The initial CARS score indicator in each group was at the level of 45. In Groups 1 and 2, there were improvements in behaviour defined for the "Attitude to people", "Body use", "Visual response", "Taste, smell, the reaction on touch and use" and "General Impressions" sub-scales. Those changes were not observed in the control group. The research study proved the safety and effectiveness of the use of cord blood mononuclear cells in the complex treatment of patients. (Transplantation of human cord blood mononuclear cells and umbilical cord-derived mesenchymal stem cells in autism Yong-Tao Lv, Yun Zhang, Min Liu,¹ Jia-na-ti Qiuwaxi,² Paul Ashwood,³ Sungho Charles Cho,⁴ Ying Huan,¹ Ru-Cun Ge,¹ Xing-Wang Chen,¹ Zhao-Jing Wang,² Byung-Jo Kim,⁵ and Xiang Hucorresponding).

\

CLINICAL PURPOSES

Estimation of the safety and efficiency of the method of transfusion of umbilical blood hemopoetic cells to patients with diagnosed autism spectrum disorder without depending on the degrees of compatibility of donor and recipient.

TASKS

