Evaluation scales CARS, ATEC (to assess the dynamics). Neuropsychological examination, examination of a speech therapist-pathologist. Assessment of neurological status. Determination of the immune status by flow cytometry (CD3; CD4; CD8; CD19; CD16-56). Determination of the level of cytokines in peripheral blood: interleukin 1 beta, interleukin 6, tumor necrosis factor alpha, interleukin 8, gamma interferon. Determination of the HLA genotype of the subject parents and siblings.

The results will be statistically processed using parametric and non-parametric statistics methods using STATA version 9.0, Statistica for Windows version 6.0 and MS Office Excel 2007. Changes from the start of therapy and after 1, 2, 6, 12 months will be compared using the Wilcoxon criterion, comparing data between the main group and the control group using non-parametric method, using the Mann-Whitney test (data are presented in Me - median format with an indication of 25% (q1) and 75% (q3) quartile.

Treatment protocol

Selection of patients and assessment of their psychological status, transfusion of umbilical cord blood HSC in the conditions of day hospital is carried out by specialists of the State budgetary institution of public health "Samara Regional Children's Clinical Hospital N.N. Ivanova Laboratory examination, selection of biomaterial will be carried out by the State Budgetary Institution "MC Dynasty".

Stage 1 - selection and examination of the patient, determination of indications and contraindications to this method of treatment is carried out by a child neurologist, pediatrician (pediatrician), medical psychologist. Assessment of autism disorder is carried out according to the assessment scales of CARS, ATEC.

A prerequisite for inclusion:

- diagnosed with autism spectrum disorder by a psychiatrist,
- Dispensary supervision by a child psychiatrist at the place of residence.

Mandatory general clinical trials (clinical and diagnostic laboratory):

- a) General clinical blood tests (erythrocytes, hemoglobin, platelets, clotting time, leukocytes + formula, COE) - shelf-life 14 days.
- b) general clinical urine test - shelf life 14 days.
- c) feces per helminth eggs - shelf life 14 days.
- d) blood type and rhesus factor.

A patient who meets the selection criteria and has no contraindications for this type of treatment enters into a protocol and signs an informed consent (or his/her legal representative).

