The results will be statistically processed using parametric and non-parametric statistics methods using STATA version 9.0, Statistica for Windows version 6.0 and MS Office Excel 2007. Changes from the start of therapy and after 1, 2, 6, 12 months will be compared using the Wilcoxon criterion, comparing data between the main group and the control group using non-parametric method, using the Mann-Whitney test (data are presented in Me - median format with an indication of 25% (q1) and 75% (q3) quartile.

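### The 10 v 10 non-randomised comparison rests on an unadjusted Mann-Whitney test of unspecified 'data'; naming one scale, one visit and a baseline-adjusted analysis would gain precision at little cost

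*Combined protocol and SAP*

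**What the plan says.** Object of study and Statistical considerations describe an interventional, prospective, non-randomised study of 10 treated children and 10 controls. The controls are to be comparable in age, gender and degree of disorder, by a 'paracopy' type that is not defined.

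Research methods and the last paragraph of Statistical considerations carry the same analysis text. Within groups: "Changes from the start of therapy and after 1, 2, 6, 12 months will be compared using the Wilcoxon criterion". Between groups: "comparing data between the main group and the control group using non-parametric method, using the Mann-Whitney test". Parametric methods are mentioned, but none is specified.

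On scales, Research methods lists "Evaluation scales CARS, ATEC (to assess the dynamics" without ranking the two, and Stage 1 of the Treatment protocol scores patients on both at entry. The baseline summary names age, sex and ATEC only. Therapy evaluation criteria adds: "Evaluation of the effect is carried out using the scales used in the introduction to the protocol".

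There are three visit lists:
- months 1, 2, 6 and 12 in the analysis text;
- "Evaluation of the effect of treatment is carried out 1, 2, 3 and 6 months after treatment" in Therapy evaluation criteria;
- months 1, 2, 3, 6 and 12 after the initial infusion in Statistical considerations, which speaks of primary outcomes in the plural and names none.

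**The concern.** Selecting controls for comparability can leave a baseline difference between two groups of 10. How far that difference enters the result depends on whether the Mann-Whitney test is run on follow-up scores or on changes, and the plan does not say. Even with no baseline difference, the two readings differ in precision, because one of them discards the baseline score.

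The choice is wide. Two scales, four visits and two meanings of 'data' give 2 x 4 x 2 = 16 comparisons that fit the sentence. With the five-visit list it is 2 x 5 x 2 = 20. If 'paracopy' means 1:1 pairs, the Mann-Whitney test also ignores the pairing.

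**Working it through.** **Inputs.** From the documents: 10 v 10, non-randomised, Mann-Whitney. The documents give no alpha, SD, target effect or baseline/follow-up correlation, so the sample size cannot be reproduced. Assumed: normal scores with SD 1 at both times, two-sided 5%, and correlation r = 0.5/0.7/0.85. Mann-Whitney is exact (reject if U is at most 23 or at least 77, true size 4.3%). ANCOVA is a t-test on 20 - 3 = 17 df. Each setting has 40,000 simulated trials. Matching, where modelled, is 1:1 on severity with an assumed within-pair SD of 0.3.

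**Why the analyses differ in precision.** The SD of the quantity compared, at r = 0.5/0.7/0.85, is:
- follow-up score: 1/1/1;
- change: sqrt(2(1 - r)) = 1.00/0.77/0.55;
- ANCOVA residual: sqrt(1 - r^2) = 0.87/0.71/0.53.

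**Power at a 0.8 SD effect, no baseline difference (%), r = 0.5/0.7/0.85**

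| Analysis | Unmatched | Matched 1:1 on severity |
|---|---|---|
| Mann-Whitney, follow-up | 35/35/35 | about 34/32/31 |
| Mann-Whitney, change | 35/54/83 | about 34/54/84 |
| ANCOVA | 47/63/87 | about 50/65/89 |

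Held to the 4.3% size of the exact Mann-Whitney, unmatched ANCOVA still has 45/61/86%. At r = 0.7, unmatched, Mann-Whitney on follow-up and on change reach different significance verdicts in 41% of trials.

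**Scale of a plausible effect.** The earlier study in the background text reports: "in Group 1, the indicator decreased by 20.0%; in Group 3, i.e. the control group, the indicator decreased by 13.7" per cent. It also states: "The initial CARS score indicator in each group was at the level of 45". The difference is 45 x (0.200 - 0.137) = 2.8 points, which is 2.835/7 = 0.4 SD to 2.835/3.5 = 0.8 SD if the SD is 7 to 3.5 points (assumed). That study used another regimen, so this is only an illustration. At 0.4 SD, unmatched power is 12/12/12% (follow-up), 12/17/30% (change) and 15/21/35% (ANCOVA).

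**Bias from a leftover baseline difference s, shown at s = 0.35 SD and r = 0.7**

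| Assumption | Follow-up | Change | ANCOVA |
|---|---|---|---|
| Children with equal baselines have equal expected follow-up | r x s = +0.25 | (r - 1) x s = -0.10 | 0 |
| The group gap is stable over time | s = +0.35 | 0 | (1 - r) x s = +0.10 |

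Follow-up scores are biased in both rows. Change and ANCOVA are each unbiased in one.

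**False positives at s = 0.35 SD (%), r = 0.5/0.7/0.85**

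| Setting | Follow-up | Change | ANCOVA |
|---|---|---|---|
| Unmatched, equal-baseline | 5.7/7.1/8.6 | 5.7/5.1/4.8 | 5.0/5.0/5.2 |
| Unmatched, stable gap | 10/10/10 | 4.4/4.4/4.2 | 7.1/6.1/5.4 |
| Matched, equal-baseline | 3.7/2.7/1.7 | 3.5/3.7/4.0 | about 5 |
| Matched, stable gap | 7.4/4.9/2.6 | 2.3/3.2/3.7 | 7.1/6.1/5.5 |

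With matching, a test that ignores the pairs becomes conservative, and this offsets much of the bias in the rejection rate. The bias in the estimate remains.

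**The case against.** **The design already deals with baseline severity.** Controls are to be comparable in degree of disorder, and with close matching the raw follow-up test mostly rejects a true null less often than ANCOVA does. This stands. A reader might infer that the planned test has an inflated false-positive rate. The documents do not support that in general, because they promise comparability on severity and leave its tightness open.

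**The sentence means changes.** It may: the clause before it is about changes. If so, the loss against ANCOVA is small when r is high (83% v 87% at r = 0.85). The scale, visit, time origin and pairing would still be open.

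**ANCOVA is a preference.** In part this is true. At 0.35 SD unmatched, the worst false-positive rate is 7.1% for ANCOVA and 5.7% for change. With skewed errors ANCOVA's power gain over change goes (54/68/87% v 45/69/90%, better only at r = 0.5). A reader might infer that ANCOVA is the one correct analysis. The documents cannot show which bias assumption holds, so the case for it is precision, with change scores reported beside it.

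**The scales do not conflict.** A reader might infer that effect evaluation is tied to CGI and ABC, because the background text says "during the research studies the CARS, CGI and ABC scales were used". That sentence appears to describe earlier research. In translated text, the scales of the introduction to the protocol may be those used at entry, which are CARS and ATEC. The wording needs clarifying, but it does not establish a contradiction.

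**A study of 20 cannot conclude much anyway.** True: at 0.4 SD power is only 15-35% even after the change. That is a reason not to discard baseline information already collected.

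**Conclusion.** The point holds as a cheap improvement in precision and pre-specification. The plan names one unadjusted between-group test, does not say what it is applied to, and ranks no scale or visit. Under the assumed inputs, moving from follow-up scores to ANCOVA raises power at 0.8 SD from about 35% to 47-87% without matching, and from about 31-34% to 50-89% with it. If 'data' already means changes, the gain is 12, 9 and 4 percentage points at r = 0.5, 0.7 and 0.85 without matching (47 - 35, 63 - 54, 87 - 83), and may be nil with skewed errors.

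A leftover baseline difference biases raw follow-up scores under both assumptions examined. Its effect on false positives depends on matching that the plan does not define. All sizes rest on assumed values of alpha, SD, r and matching tightness. No analysis here protects against unmeasured confounding from non-random allocation.

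**What to change.** In Research methods and the last paragraph of Statistical considerations, before outcome data are seen, replace the Mann-Whitney clause with wording such as:

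> The main between-group comparison is of [CARS or ATEC] total score at 6 months from [one stated origin, defined for both groups], by ANCOVA on group and the baseline value of that scale, giving the adjusted difference and 95% CI. Mann-Whitney on change from baseline is reported alongside. Other scales and visits are secondary.

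Month 6 is the latest visit in all three lists, but the sponsor may choose another. The origin must be stated because, with three infusions a month apart, counting from the first or from the last differs by about two months.

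Also:
- Score controls on the chosen scale at baseline and at the same visits, and include its baseline value in the baseline summary.
- State whether 'paracopy' means 1:1 pairs. If it does, record pair identity and use a baseline-adjusted paired analysis in place of the unpaired ANCOVA.
- Say which scales the reference to the introduction means.

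**Cost.** Mostly SAP wording, plus scoring of controls and a pair identifier where these are not already planned. ANCOVA assumes linearity at n = 20 and is off by (1 - r) x imbalance if the group gap is stable. The two analyses reach different significance verdicts in about 17% of trials at 0.8 SD and r = 0.7 (unmatched), so estimates and intervals should be compared, not p-values. A paired analysis costs error degrees of freedom: regressing pair differences on baseline differences leaves 10 - 2 = 8, against 17. The adjusted 95% CI is still about +/-0.68 SD at r = 0.7, or 0.68 x 3.5 = 2.4 to 0.68 x 7 = 4.8 CARS points at the assumed SDs, beside the illustrative 2.8-point effect.
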